3.4.1 Phase 2 Efficacy Endpoints – Month 6 Analysis

3.4.1.1 Phase 2 Primary Efficacy Endpoint in the US (Secondary Endpoint Outside the US)

The primary efficacy endpoint in the US (secondary outside the US) is symptom-based clinical response assessed by MACrO₂ PRO between baseline and Month 3 and baseline and Month 6. While summary results for both of these visits will be generated in parallel, the Month 6 visit will be considered of primary interest with the Month 3 visit considered supportive. The Estimand corresponding to the primary endpoint is defined with the following five attributes:

1. Population: Randomized patients with MAC culture-positive Pre-Study and Screening respiratory specimens
2. Treatment: Epetraborole oral tablets 500 mg (two 250 mg oral tablets) QD + OBR or placebo oral tablets QD matched to epetraborole dosage + OBR
3. Variable: MACrO₂ PRO response rate at Month 3 and Month 6. MACrO₂ PRO response at the given time point is defined as improvement of ≥ 1 grade in the key symptom with no worsening of other symptoms compared with baseline MACrO₂ PRO assessment. The baseline MACrO₂ PRO assessment is defined as the last assessment prior to the first dose of study drug.
4. Intercurrent events:
 - a. New, additional non-study-specific, antimycobacterial therapy that is potentially effective against MAC for reasons other than clinical failure of study drug: data collected after such therapy will not be used and patients will be classified as a clinical failure for MACrO₂ PRO response (composite strategy)
 - b. Surgery for MAC lung disease for reasons other than clinical failure of study drug: data collected after such surgery will not be used and patients will be classified as a clinical failure for MACrO₂ PRO response (composite strategy)
 - c. Permitted medications/interventions or prohibited medications/interventions other than those described in bullets a and b: MACrO₂ PRO data collected after permitted or other prohibited medications/interventions administration will be used as recorded (treatment policy strategy)
 - d. Inadequate compliance: patient data will be used as recorded (treatment policy strategy)
5. Population-level summary: Difference between epetraborole + OBR and placebo + OBR in response rate in MACrO₂ PRO assessment at Month 3 and Month 6.

MACrO₂ PRO item scores will be summarized by visit in the Micro-ITT Population, using visits of day 1 (randomization/baseline), Month 3 (day 83 ± 7 days) and Month 6 (day 169 ± 7 days). Summaries of the number and percentage of patients in each severity category (or missing results) for each symptom, by treatment arm and overall for all patients in the Micro-ITT Population, according to patient-reported entries in the MACrO₂ PRO, will be produced.

MACrO₂ PRO response is defined as improvement of ≥ 1 grade in the key symptom with no worsening of other symptoms. Descriptive statistics (n, %) will be presented by treatment group, along with the treatment difference (i.e. epetraborole + OBR response percentage minus placebo + OBR response percentage), associated 95% confidence interval and p-value, calculated using the method of Miettinen and Nurminen (see Appendix), both including (primary analysis) and excluding (sensitivity analysis) stratification by baseline ALIS use and age (<65 years versus ≥ 65 years). As the Month 6 visit will be considered of primary interest while the Month 3 result will be considered supportive, no corrections for multiple comparisons are proposed to the corresponding p-values or confidence intervals for these endpoints. As further supportive analyses, corresponding results of the above analyses will be generated in the PP Population.

Patients who receive new, additional non-study-specific, antimycobacterial therapy that is potentially effective against MAC for reasons other than clinical failure of study drug (in treating the index MAC lung infection) will be classified as a clinical failure for the analysis in the Micro-ITT Population and will be excluded from the PP Population. Patients who fail to provide a complete MACrO₂ PRO assessment of all symptoms at the specific Month 3 or Month 6 time point will be classified as a clinical failure for the analysis at that time point for all populations.

3.4.1.2 Phase 2 Primary Efficacy Endpoint Outside the US (Secondary Endpoint in the US)

The primary efficacy outside the US (secondary in the US) is by-patient sputum culture conversion monthly through Month 6. The Estimand corresponding to the primary endpoint is defined with the following five attributes:

1. Population: Patients with MAC culture-positive Pre-Study and Screening respiratory specimens
2. Treatment: Epetraborole oral tablets 500 mg (two 250 mg oral tablets) QD + OBR or placebo oral tablets QD matched to epetraborole dosage + OBR
3. Variable: Sputum conversion rate is defined as proportion of patients having culture conversion based on 3 consecutive monthly negative sputum cultures for MAC by Month 6
4. Intercurrent events:
 - a. New, additional non-study-specific, antimycobacterial therapy that is potentially effective against MAC for reasons other than clinical failure of study drug: data collected after such therapy will not be used and patients will be classified as a failure for microbiological response (composite strategy)
 - b. Surgery for MAC lung disease for reasons other than clinical failure of study drug: data collected after such surgery will not be used and patients will be classified as a failure for microbiological response (composite strategy)
 - c. Permitted medications/interventions or other prohibited medications/interventions other than those described in bullets a and b: microbiological response data collected after permitted or other prohibited medications/interventions administration will be used as recorded (treatment policy strategy)
 - d. Inadequate compliance: patient data will be used as recorded (treatment policy strategy)
5. Population-level summary: Difference between epetraborole + OBR and placebo + OBR in sputum conversion rate by Month 6.

“Microbiological response” is defined as sputum culture conversion based on 3 consecutive monthly negative sputum cultures for MAC by Month 6. By-patient microbiological response will be presented for the Micro-ITT Population by Month 6. Descriptive statistics (n, %) will be presented by treatment group, along with the treatment difference (i.e. epetraborole + OBR response percentage minus placebo + OBR response percentage), associated 95% confidence interval and p-value, calculated using the method of Miettinen and Nurminen, both including (primary analysis) and excluding (sensitivity analysis) stratification by baseline ALIS use and age (<65 years versus ≥65 years).

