It is anticipated that the primary endpoint in the US will be MACrO₂ PRO symptom-based clinical response at Month 3 for the Phase 3 part of the study. However, whether this time point for the primary endpoint is at Month 3 or Month 6 will depend upon the psychometric evaluation of the PRO and the results of the Phase 2 part of the study. Outside of the US, the primary endpoint will be microbiological culture conversion by Month 6.

Study assessments and procedures will be completed at the following visits for both Phase 2 and Phase 3 parts of the study:

- **Screening Visit:** Screening assessments to determine study eligibility will be performed within 8 weeks prior to randomization as shown in [Table 3](#) in [Appendix A](#). Two to 3 sputum samples will be collected during Screening and may be collected on the same day or within a 5-day window beginning with collection of the first sample. See [Section 7.5.3](#) for additional details.
- **Treatment Period:** Day 1 to EOT; the treatment period for each patient will vary, up to a maximum of 16 months, depending on the patient's sputum culture results; see details in [Section 3.1.1](#).
 - During the first 6 months of the Treatment Period, study assessments (including microbiological, clinical, safety, and PK assessments) will be performed from Day 1 (calendar day of first dose of study drug) and every 28 days (± 7 days) thereafter, up to Month 6 (Day 169 ± 7 days).
 - Patients who culture-convert based on 3 consecutive monthly negative sputum cultures for MAC by Month 6 (Day 169 ± 7 days) will continue blinded study drug for 12 months from the first month that defines sputum culture conversion up to a maximum of 16 months in total; see [Section 3.1.1](#).
 - For patients continuing blinded study drug during the Treatment Period after Month 6, safety assessments will be performed monthly, and other assessments (including microbiological and clinical assessments) will be performed every 3 months (84 days ± 7 days), up to EOT, as specified in [Table 4](#) in [Appendix A](#).

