3 STATISTICAL METHODOLOGY

3.1 General Considerations

3.1.1 Analysis Day

Study days are calendar days, rather than 24-hour days. Analysis day will be calculated from the date of first dose of study drug. The day of the first dose of study drug will be Day 1, and the day immediately before Day 1 will be Day -1. There will be no Day 0. Any durations in days will be derived as event stop date – event start date + 1.

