Time (in days) to first sustained MACrO₂ PRO-based clinical response through Month 6 will be summarized by treatment group in the Micro-ITT Population. The first sustained PRO-based clinical response through Month 6 is defined as the earliest study day at which the weekly MACrO₂ assessment meets the criteria of clinical response and which is maintained consistently at all available subsequent assessments through Month 6 (inclusive). Missing assessments will be excluded from sustained response determination. A Kaplan-Meier analysis and corresponding plot will be provided by treatment, and estimated event rates by treatment arm based on the plot will be provided for study days 29, 57, 85, 113, 141, and 169 to align with protocol specified visit months. Patients who fail to achieve sustained response

by Month 6 or discontinue early from the study will be censored at their last day of treatment or the day of their Month 6 visit, whichever is earlier. In an alternative approach to assess the impact of censoring on the analysis results, the same analysis will be performed where all patients who fail to achieve sustained response and who discontinue from the study prior to Month 6 will be censored at the maximum allowable duration of 6 Months. Time to event will also be analyzed using a Cox proportional hazard model with the same variables as the previous exploratory analysis, and hazard ratio and 95% confidence intervals at Month 6 will be reported.

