Time (in months) to first negative sputum culture through Month 4 will be summarized by treatment group in the Micro-ITT Population. A Kaplan-Meier analysis and corresponding plot will be provided by treatment, and estimated event rates by treatment arm based on the plot will be provided for months 1 (Day 29), 2 (Day 57), 3 (Day 85), and 4 (Day 113). Patients who fail to achieve the endpoint by Month 4 or discontinue early from the study will be censored at their last day of treatment or the day of their Month 4 visit, whichever is earlier. In an alternative approach to assess the impact of censoring on the analysis results, the same analysis will be performed where all patients who fail to achieve the endpoint and who discontinue from the study prior to Month 4 will be censored at the maximum allowable duration of 4 Months. Time to event will also be analyzed using a Cox proportional hazard model with the same variables as the previous exploratory analysis, and hazard ratio and 95% confidence intervals at Month 4 will be reported.

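### SAP 3.4.1.1 centres the Month 3 window for the Phase 2 MACrO₂ item summaries on Day 83, but the protocol schedule and the rest of the SAP put Month 3 at Day 85

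*SAP*

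**What the plan says.** SAP 3.4.1.1 (Phase 2 primary efficacy endpoint in the US) says that MACrO₂ "item scores will be summarized by visit in the Micro-ITT Population, using visits of day 1" for baseline, "Month 3 (day 83 ± 7 days") and "Month 6 (day 169 ± 7 days"). The next paragraphs define response and then state the failure rule: a patient without a complete assessment "at the specific Month 3 or Month 6 time point will be classified as a clinical failure for the analysis" at that time point. Neither paragraph gives a day range.

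SAP 3.1.4 has its own rule for missing MACrO₂ data. It makes a patient indeterminate, and so a non-responder, when data are missing or incomplete at Month 3 or Month 6 as the protocol defines them. It applies to both phases.

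For the day count, SAP 3.1.1 says "The day of the first dose of study drug will be Day 1", with no Day 0. Protocol 3.1 says that assessments "will be performed from Day 1 (calendar day of first dose of study drug) and every 28 days" thereafter, and the schedule in Protocol Table 3 lists Month 3 as Day 85 ± 7. SAP 3.4.1.4 reports time to MACrO₂ response at "study days 29, 57, 85, 113, 141, and 169 to align with protocol specified visit months", and time to first negative culture at "months 1 (Day 29), 2 (Day 57), 3 (Day 85), and 4 (Day 113"). SAP 3.4.3.4 uses the same list of days for Phase 3.

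**The concern.** One sentence of the SAP disagrees with the protocol and with the rest of the SAP about when Month 3 is. It stands in a primary-endpoint section and is the only place where the SAP gives post-baseline MACrO₂ visits as a day with a window, so it is a natural source for whoever programs the visit assignment.

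Two things are at stake. First, the Month 3 item tables would omit some entries made on schedule and admit some made before the protocol window opens. Second, the same instrument could be given two Month 3 windows: Days 76-90 for item summaries, and the protocol's window for response and missing-data status. The item table and the response table for one visit might then rest on different entries from the same patient. MACrO₂ is completed weekly, with an extra retest a week after Month 3, so several entries can lie in the window. The SAP has no rule for choosing among them.

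**Working it through.** **Inputs**
- First dose is Day 1, no Day 0 (SAP 3.1.1).
- Visits every 28 days from Day 1 (Protocol 3.1).
- Month 3 at Day 85 ± 7 (Protocol Table 3).
- Month 3 at Day 83 ± 7 and Month 6 at Day 169 ± 7 (SAP 3.4.1.1).
- MACrO₂ weekly through Month 6; retest 1 week (+1 day) after the Month 3 visit (Protocol Table 3 and its notes).

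**Step 1: can Day 83 be reproduced?** Visit day = 1 + 28 × month.
- Months 1 to 6: Days 29, 57, 85, 113, 141, 169.
- Month 3 = 1 + 28 × 3 = 85. Month 6 = 1 + 28 × 6 = 169.

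The SAP's Month 6 figure is reproduced and its Month 3 figure is not. Other counting rules do not rescue it:
- 28 × 3 = 84.
- 28 × 3 − 1 = 83, but the same rule gives Month 6 = 28 × 6 − 1 = 167, not the 169 in the same sentence.
- Calendar months: 3 × 30.4375 = 91.3.

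No rule tried gives both 83 and 169.

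**Step 2: compare the windows.**

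| | Centre | Window | Days |
|---|---|---|---|
| SAP 3.4.1.1 | 83 | 76-90 | 15 |
| Protocol Table 3 | 85 | 78-92 | 15 |

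Days 91 and 92 are on schedule but outside the SAP window. Days 76 and 77 are inside the SAP window but before the protocol's opens. The loss is 2/15 = 13.3% of the allowed days.

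**Step 3: how many visits?** The documents give no distribution of visit days. If Month 3 visits were spread evenly over the 15 days (an assumption), 13.3% would fall on Days 91-92. If they cluster near Day 85, the share approaches 0. This is a share of visits, not of misclassified patients.

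**Step 4: would such a patient lack an entry in Days 76-90?** With weekly entries, a patient seen on Day 91 has earlier ones due about Days 84 and 77. One seen on Day 92 has them due about Days 85 and 78. All four days lie within 76-90. Only a patient who missed or left incomplete both earlier entries would have nothing in the SAP window.

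**Step 5: can the choice of entry change with nothing missing?** Suppose the entry closest to the target day is used (an assumption, since the SAP states no rule) and a patient has entries on Days 80 and 87. From Day 83 the distances are 3 and 4, so Day 80 is used. From Day 85 they are 5 and 2, so Day 87 is used.

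**Step 6: does the retest matter?** For a visit on Day 85 the retest is due on Day 92 or 93, and Day 92 is inside Days 78-92. Under the protocol window the retest can fall inside for visits on Days 78-85; under the SAP window, for visits on Days 78-83. Correcting the centre alone therefore leaves the visit entry and the retest competing in some patients.

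**The case against.** A reader might infer that Day 83 ± 7 is the window that decides response or failure, so that patients seen on Days 91-92 become failures. The text does not say so. The figure sits in a sentence about by-visit item summaries, the failure rule that follows states no days, and SAP 3.1.4 ties indeterminate and non-responder status to the protocol's time points, which points to Day 85 ± 7. This objection stands. A misclassified response would require that the item window had been borrowed for response, and the documents do not show that.

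A reader might also carry the error into Phase 3, because SAP 3.4.3.3 refers to clinical response as already defined. That reference is to the responder definition, which the section restates without any day window. No Phase 3 section uses Day 83, and the only Phase 3 mapping of months to days (SAP 3.4.3.4) has Day 85. This objection also stands.

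Finally, the practical effect is small: entries are weekly, Month 3 is declared supportive, and Month 6 is right. That is correct and sets the weight of the point. It does not remove the contradiction, and SAP 3.1.4 does not cure it either. Reading 3.1.4 as governing response leaves item tables and response tables on different Month 3 windows.

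**Conclusion.** Day 83 is wrong as written. It conflicts with Protocol Table 3, the 28-day spacing and the SAP's own Day 85, and the correct Day 169 beside it rules out a different counting convention. This part rests on no assumption.

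The certain consequence is limited to the Phase 2 Month 3 item summaries, where two on-schedule days (91-92) are excluded and two early days (76-77) admitted. Anything beyond that is conditional. If Days 76-90 was also programmed for Month 3 response, the usual effect would be that a different weekly entry is used. A patient whose only complete entry is on Day 91 or 92 would become a failure, which should be rare. The 13.3% is an illustration under evenly spread visits, with a plausible range from about 0 to that figure.

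The Month 6 result, which the SAP names as of primary interest, is not touched. This is a minor correction, worth making because it is cheap and the Month 3 outputs belong to a primary-endpoint section.

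**What to change.** Use Day 85 ± 7 (Days 78-92) as the Month 3 window, and apply it to both the item summaries and the response and failure rule. State which entry is used when several lie in the window, and exclude the Month 3 + 1 week retest whenever the visit entry exists.

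The SAP Introduction limits changes after Version 2.0 to Phase 3 and sends other deviations to the CSR, so for Phase 2 the correction belongs in the CSR. Record there which Month 3 window was programmed for the item tables and which for response. If Day 83 was used for either, rerun the affected supportive Month 3 outputs with Day 85 ± 7 and report any differences.

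The cost is one number, one sentence on choice of entry and, at most, a rerun of supportive Phase 2 tables. No new data are needed.

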3.4.1.3 Phase 2 Secondary Efficacy Endpoints at Month 6 Analysis

The secondary efficacy endpoints include microbiological response (by-patient sputum culture conversion and by-patient microbiological improvement) monthly through Month 6, PRO symptom-based clinical response (mean changes in PRO domain scores or improvement of ≥1 grade in the key symptom with no worsening of other symptoms in the MACrO₂ PRO) monthly through Month 6, concordance of clinical response and microbiological response (concordance between PRO response and microbiological response), and rates of recurrence, reinfection, and relapse by Month 6.

“Microbiological response” is defined as sputum culture conversion based on 3 consecutive monthly negative sputum cultures for MAC by Month 6; “microbiological improvement” is defined as a decrease in MAC colony counts of ≥ 1 category from baseline. By-patient microbiological response by Month 6 and by-patient microbiological improvement at Month 3 and Month 6 (see details below) will be presented for the Micro-ITT Population. Descriptive statistics (n, %) will be presented by visit and treatment group. Treatment difference, associated 95% confidence interval and p-value at Month 3 and Month 6, will be calculated using the method of Miettinen and Nurminen, both including (primary analysis) and excluding (sensitivity analysis) stratification by baseline ALIS use and age (<65 years versus ≥ 65 years).

By-patient microbiological improvement (decrease in MAC colony counts of ≥ 1 category from baseline) will be summarized using the categories of 0 = no growth on agar or broth; 1 = growth in broth only; 2 = 1 to 49 CFU/mL; 3 = 50 to 99 CFU/mL; 4 = 100 to 199 CFU/mL; 5 = 200 to 299 CFU/mL; 6 = ≥ 300 CFU/mL, where specific colony counts are based on solid agar growth. If more than one sputum sample at the same visit is culture positive for the same species of MAC, the culture with the highest colony count will be used for determination of microbiological improvement.

Descriptive statistics of both the reported scores (and change from baseline for continuous scores) will be reported by visit (monthly through Month 6) for scores for all other PROs collected in the study (QOL-B, NTM Symptoms Module, SGRQ-C, PGIS, PGIC, CGIS, CGIC, and Meaningful Change Question) based on the Micro-ITT Population. Change from baseline score at Month 3 and Month 6 of selected continuous PROs including QOL-B respiratory domain score, NTM Symptoms Module domain score, and SGRQ-C total score will be analyzed using an analysis of covariance (ANCOVA) model, including baseline score, treatment and stratification factors (baseline ALIS use and age (<65 years versus ≥ 65 years)) as covariates. Least squares means, 95% confidence intervals, and p-values of the treatment comparison will be presented for both Micro-ITT and PP populations.

Clinical response as defined above for the MACrO₂ PRO as well as for each additional PRO measure according to pre-defined response thresholds relative to baseline will be examined monthly through Month 6. Response in QOL-B respiratory domain score is defined as an improvement in QOL-B respiratory domain score of ≥ 8 based on a minimally clinically important difference (MCID) established for bronchiectasis patients ([Quittner 2015b](#)), as well as by a threshold to be determined as part of a blinded anchor-based psychometric analysis of the observed QOL-B respiratory domain scores across pooled treatment arms and visits as a potentially more specific indicator of meaningful improvement in treatment-refractory MAC patients. Response in SGRQ-C total score is defined as an improvement in SGRQ-C total score of ≥ 4 based on a MCID established for COPD patients ([Jones 2023](#)). A corresponding threshold for a response endpoint in the NTM Symptoms domain of the NTM Module has not been defined, as an MCID has yet to be clearly established for this endpoint, but this study will investigate distribution-based minimal important differences (MIDs) using $0.5 \times$ baseline SD and the standard error of the mean (SEM) of the baseline measurement, where in both cases baseline is pooled across both treatment groups in the Micro-ITT Population, as experimental response thresholds. Response in PGIS or CGIS at each post-baseline visit is defined as a reduction in severity of one or more grades relative to baseline. Response in PGIC or CGIC at each post-baseline visit is defined as a reported change of severity category of “Much Better” or “A Little Better.” For all of the above PRO response definitions, missing results at the given timepoint will be considered failures in the Micro-ITT analysis.

Clinical response as defined above for each individual PRO endpoint (MACrO₂, QOL-B respiratory domain, SGRQ-C, NTM Symptoms Module, PGIS, CGIS, PGIC, and CGIC) will be presented dichotomously (Yes/No) for each treatment arm and will be presented as the treatment difference and associated 95% confidence interval and p-value, calculated using the method of Miettinen and Nurminen

stratified by baseline ALIS use and age (<65 years versus ≥65 years) for both the Micro-ITT and PP populations. In addition, to examine the influence of baseline severity on the treatment effect, clinical response rate by month will also be analyzed using a logistic regression model, including treatment and baseline key symptom severity (for MACrO₂ only), baseline score (for QOL-B respiratory domain, SGRQ-C Total Score, NTM Symptoms Domain), baseline severity in CGIS (for CGIS and CGIC), or baseline severity in PGIS (for PGIS and PGIC) as covariates. Stratification factors of baseline ALIS use and age (<65 years versus ≥65 years) will also be included as covariates in each model. For each logistic regression model, the estimated odds ratio and 95% confidence interval and corresponding p-value for the treatment effect will be presented.

Line plots of mean score (+/- SD) over time will be produced for continuous PROs (e.g., QOL-B domain score, NTM symptom module score and total SGRQ-C score), with the two treatment groups indicated with different colors on the plot. A bar plot of categorical PROs (e.g., proportion of MACrO₂ responders, individual and key MACrO₂ symptoms, PGIS, PGIC, CGIS, CGIC and Meaningful Change Question) by treatment group will also be produced by visit.

In order to assess the concordance of PRO changes with microbiological changes the following summaries will be produced for each PRO in the Micro-ITT Population. These will be produced at Months 3 and 6, as specifically noted below:

- Summary of PRO response (Response/Failure) versus sputum culture conversion (Conversion/No Conversion) by Month 6
- Summary of PRO response (Response/Failure) at Month 3 versus sputum culture conversion (Conversion/No Conversion) by Month 6
- Summary of PRO response (Response/Failure) versus microbiological improvement (Improvement/No Improvement/Non Applicable Due to Missing Baseline CFU Score) at Months 3 and 6
- Summary of PRO response (Response/Failure) versus microbiological colony count culture categories (Missing, 0, 1, 2, 3, 4, 5, 6) at Months 3 and 6

Rates of recurrence, relapse, and reinfection following two different definitions will be presented by Month 6 in the Micro-ITT Population. The primary analysis of recurrence, relapse, and reinfection will use the following definitions derived from the NTM-NET consensus statement ([van Ingen 2018](#)) regarding treatment outcome definitions in NTM pulmonary disease:

- Recurrence is defined as at least 1 MAC-positive culture on any media type (broth or agar) for 2 consecutive visits after culture conversion. Recurrence will be further categorized as either reinfection or relapse as follows:
 - Re-infection: at least 1 MAC-positive culture of a different species or the same species but a different strain of the causative species for 2 consecutive visits after culture conversion
 - Relapse: at least 1 MAC-positive culture of the same strain as the causative species for 2 consecutive visits after culture conversion

A sensitivity analysis will also be performed using the following definitions from the CONVERT trial ([Griffith 2021](#)):

- Recurrence is defined as having MAC-positive sputum cultures after culture conversion in liquid broth media (agar negative) for 3 or more consecutive visits, or having 1 MAC-positive sputum culture on solid media (LJ and/or 7H11 agar positive). Recurrence will be further categorized as either reinfection or relapse as follows:
 - Reinfection: new infection with a different MAC species or the same MAC species but a different strain from that isolated at baseline
 - Relapse: same MAC species and strain that was isolated at baseline

At the time of Month 6 database lock, only overall recurrence rates by either definition will be presented. Further subdivision into relapse versus reinfection within each definition of recurrence will be determined by whole genome sequencing when available. Identification of the overall recurrence, reinfection and relapse will be determined by a Sponsor Pathogen Review Committee in accordance with the Pathogen Review Plan.

